5.5 Study Days

Study days of an event/assessment is defined as the date of the event/assessment minus the date of Study Day 1. If the result is a positive number or zero, add one day.

All derivations of duration are initially done based on days and converted to weeks, months and years if needed using 7, 30.4375 and 365.25, respectively, as denominator, if not otherwise specified.

5.6 Subject Cohorts for Presentation

All CL202 subjects will be classified into one of the three non-overlapping cohorts in analysis presentations:

- UX007/trihep naïve subjects. This cohort consists of subjects who had no prior exposure to UX007/trihep before enrolling into CL202. However if a subject participated in a prior UX007/trihep study but was off UX007/trihep for more than two years before enrolling into this study, then this subject will be treated as a naïve subject and historical major clinical events will be collected.
- UX007-CL201 rollover subjects. This cohort consists of subjects who rolled over from UX007-CL201 to UX007-CL202 study.
- Other. This cohort includes subjects unassigned to the above two cohorts, i.e., subjects from [name] Comp sites, OHSU site, eIND program and etc.

A subject may have participated in more than one prior UX007/trihep studies/programs, and the cohort that the subject will be assigned to is determined based on the following priority order: UX007-CL201 rollover subjects and Other.

5.7 Baseline

Baseline is defined as the last valid assessment prior to or on study day 1. This baseline definition will be used for all safety assessments.

5.8 UX007 Treatment Baseline

For UX007-CL201 rollover subjects, a second baseline is defined as the last valid assessment prior to or on UX007-CL201 from which they were enrolled. This baseline is referenced as UX007 treatment baseline in analysis presentations, if applicable.

5.9 Visits

The nominal visits according to schedule of assessment will be used for by-visit summaries. Assessments are assigned to visits using the visit labels in SDTM. In general, all summary tables by visit include all scheduled assessments as per Schedule of Events (Appendix 11.5).

5.10 Study Periods

A study period defines the period of time over which efficacy and safety parameters are reported in this study. There will be three types of study period used in statistical analysis.

5.10.1 Study Period 1 (Main Study Period)

Study period 1, or the main study period, starts from study day 1 till the last visit day in CL202. The last visit date is the last date among the early termination visit date, the study completion visit date, the safety follow up visit date, or the last visit date as of a clinical cutoff date, if applicable. Study period 1 will be used for all efficacy on FAS and safety analyses unless otherwise specified.

5.10.2 Study Period 2

Study period 2 has the same ending date as Study period 1 but starts from UX007 treatment day 1. Study period 2 will be used in select analyses for UX007-CL201 rollover subjects.

[figure not shown]
5.10.3 Study Period 3

Study period 3 starts from the 18 months (548 days) preceding UX007 treatment day 1 and ends 1 day prior to UX007 treatment Day 1. Study Period 3 is referred as the retrospective period for MCE data collection.

Study period 3 will be used for UX007-CL201 rollover subjects and UX007/trihep naïve subjects only in select analyses.

The following figure illustrates the definitions of the three study periods.

Figure 5.10.3.1: Diagram of Study Periods in CL202

Study Period 1 is defined for all enrolled subjects in CL202; Study Period 2 is defined for CL201 rollover subjects only; Study Period 3 is defined for CL201 rollover subjects and UX007/trihep naïve subjects. CL201 treatment period exists for CL201 subjects only;

5.11 Annualized Event Rate

The numbers of MCE will be annualized for each subject using the following formula:

$$\text{Annualized Event Rate} = \frac{\text{Number of events}}{\text{Duration of data collection period in days}/365.25}$$

The number of MCEs will be derived as the total number of events as recorded in the major clinical event CRF that occurred during the specific data collection period. Whenever an annualized rate is calculated over study period 1, the number of days is calculated from study day 1 till the data cutoff date or the early termination/study completion visit date for subjects who have early terminated/completed the study.

Annualized event rates will be calculated for MCEs overall and for each event type (ie., rhabdomyolysis, hypoglycemia, and cardiomyopathy respectively).

5.12 Annualized Duration Rate

The total duration in number of days of MCEs will be calculated and annualized for each subject using the following formula:

$$\text{Annualized Duration Rate} = \frac{\text{Total duration (days) of events}}{\text{Duration of data collection period in days}/365.25}$$

The number of days during the data collection period is determined in the same way as for annualized event rate.

Annualized duration rates will be calculated for MCEs overall and for each event type (ie., rhabdomyolysis, hypoglycemia, and cardiomyopathy respectively).

5.13 Age at Enrollment

Unless otherwise specified, the age will be derived based on the informed consent date in CL202: Age = (Inform Consent Date (ICF) – Birth Date +1)/365.25. The age will be rounded down to the nearest years and kept to one (1) decimal place. When date of birth is missing, the age recorded on CRF will be used.

5.14 Age at First Dose of UX007/triheb

The age at first dose of UX007/triheb will be derived for subjects with known date of first dose of UX007/triheb.

5.15 Total Duration of UX007 Exposure

For each subject, the total duration of UX007 exposure is defined as sum of duration in the UX007 treatment regimen log. For each analysis, the total duration will be calculated up to last visit date as of the specified clinical cutoff date or the early termination/study completion date, whichever is earlier.

5.16 % of Daily Caloric Intake Provided by Prescribed UX007 Dose

For each subject, an overall average percent of daily caloric intake provided by prescribed UX007 dose will be derived using the UX007 treatment log based on the following rules:

- Percent of daily caloric intake provided by prescribed UX007 dose will be as entered in that entry of the UX007 treatment regimen log for the duration between the start and stop dates when a single log entry has no duplicates with same start and stop date.

- For multiple log entries with same start date and same stop date, the total percent of daily caloric intake is the sum of percent of daily caloric intake of those log entries for that duration.
- Duration is defined as stop date – start date + 1 for each entry in the UX007 treatment log. If a treatment log has a stop date after the specified clinical cutoff date, the duration will be calculated as clinical cutoff date – start date + 1 for each entry in the UX007 treatment log .

Overall average percent of daily caloric intake = Sum of (percent of daily caloric intake * duration) / Sum of duration in the UX007 treatment regimen log.

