5.17 Overall Average Prescribed UX007 Dose

For each subject, an overall average prescribed UX007 daily dose in mL will be derived using the UX007 treatment log according to the following rules:

- Daily dose will be the field “Total Daily Prescribed Dose” in that entry of the UX007 treatment regimen log for the duration between the start and stop dates when the one log entry has no duplicates with same start and stop date.
- For multiple log entries with same start date and same stop date, the daily dose is the sum of the field “Total Daily Prescribed Dose” of those log entries for that duration.
- Duration is defined as stop date – start date + 1 for each entry in the UX007 treatment log. If a treatment log has a stop date after the specified clinical cutoff date, the duration will be calculated as clinical cutoff date – start date + 1 for each entry in the UX007 treatment log.

Overall average prescribed daily UX007 dose = Sum of (the daily dose * duration) / Sum of duration in the UX007 treatment regimen log

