8.4 Investigational Product Administration

8.4.1 UX007 Dosing, Exposure, and Diet

UX007 dosing and exposure parameters will be summarized based on UX007 treatment regimen log. Descriptive summary statistics will be produced for the following parameters.

- Total duration of UX007 exposure
- Overall average prescribed UX007 dose
- % of daily caloric intake provided by prescribed UX007 dose
- Total daily prescribed dose in mg/kg/day

In addition, % of daily caloric intake provided by daily UX007 intake will be derived using the 3-day average based on the 3-day diet diary. Daily caloric intake (total calories per kg), daily protein intake (% of total caloric intake), daily carbohydrate intake (% of total caloric intake), daily total fat intake (% of total caloric intake), and daily UX007 intake (% of total caloric intake) will be summarized by visit using descriptive statistics.

Profile figures for individual subjects will be generated to display dietary parameters along with the occurrence of MCEs on the same plot, over the combined pre- and post- UX007 treatment period. Prescribed %DCI of the macronutrient intakes (UX007, MCT, other fat, carbohydrates, and protein) and total caloric intake (TCI) will be displayed over time

Data listings will be generated displaying the 3-day average subject diet diary parameters which includes fat, carbohydrates, and protein measured in g/kg/day and %DCI will be provided for the CL201-Rollover and the Naïve Cohort separately.

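### SAP 5.15 sums treatment-log durations with no rule for concurrent entries, and the combining rule in 5.16 and 5.17 does not reach partly overlapping entries

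*SAP*

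**What the plan says.** Section numbers follow the body of the SAP; its table of contents lists these sections one number lower.

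- **SAP 5.15 (total exposure).** For each subject, "the total duration of UX007 exposure is defined as sum of duration in the UX007 treatment regimen log". The section adds an end date and nothing on entries that run at the same time.
- **SAP 5.16 (percent of daily caloric intake).** For entries that share both dates, "the total percent of daily caloric intake is the sum of percent of daily caloric intake of those log entries for that duration". Duration is set entry by entry: "Duration is defined as stop date – start date + 1 for each entry in the UX007 treatment log". The average is "Sum of (percent of daily caloric intake * duration) / Sum of duration in the UX007 treatment regimen log".
- **SAP 5.17 (prescribed dose in mL).** The parallel rule begins "For multiple log entries with same start date and same stop date, the daily dose is the sum of the field" and names the total daily prescribed dose. The average is "Sum of (the daily dose * duration) / Sum of duration in the UX007 treatment regimen log".
- **SAP 8.4.1 (use).** "UX007 dosing and exposure parameters will be summarized based on UX007 treatment regimen log", by descriptive statistics.

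**The concern.** A rule for entries with identical dates is needed only if the log can hold several entries for the same days. Having recognised this, the SAP combines the percent or dose but does not say that the durations are combined as well. Section 5.15 has no combining rule and does not refer to 5.16. The denominators of 5.16 and 5.17 use the same expression as 5.15, and duration is defined per entry. No section deals with entries that overlap in part or share only one date.

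Exposure duration is a basic output of a long-term safety study, and version 2.0 of the SAP adds a summary of treatment duration for pediatric subjects. Counting days twice makes the safety experience look longer than it was. Where it enters the denominator of an average, it also pulls the prescribed percent of calories down, and that figure will be read against the 25-35% target in SAP 3.2. Both shifts would depend on how a site split its log entries, not on what was prescribed.

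**Working it through.** The SAP gives no exposure or dose figure to reproduce, so the check applies its formulas to small logs. **All log values are assumptions for illustration.** Each log covers 360 calendar days, and percents are of daily caloric intake. Overlapping entries are taken to be prescriptions that really ran together.

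**Formulas**
- Entry duration (5.16, 5.17): stop − start + 1.
- Exposure (5.15): sum of durations.
- Average (5.16, 5.17): sum of (percent × duration) / sum of durations.
- Reference: exposure is the number of distinct days covered; the average is the mean over those days of the summed percent.

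**Sequential entries** (25% on days 1-180, 30% on days 181-360)
- SAP: 180 + 180 = 360 days; (25×180 + 30×180)/360 = 27.5%.
- Reference: the same. There is no error.

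**Identical dates** (15% and 15%, both on days 1-360; reference 360 days, 30%)

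| Reading | Exposure | Average |
|---|---|---|
| One merged record with one duration | 360 days | 30×360/360 = 30% |
| Percents combined in the numerator, every duration kept in the denominator | 720 days | 30×360/720 = 15% |
| Every entry kept with its own percent | 720 days | (15×360 + 15×360)/720 = 15% |
| Every entry kept, each carrying the summed percent | 720 days | 30×720/720 = 30% |

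The merged reading is right on both counts, provided that the merged records also feed 5.15. The text of 5.15 does not say that they do.

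**Partial overlap** (15% on days 1-360, 15% on days 181-360)
- Durations: 360 + 180 = 540 days.
- Numerator: 15×360 + 15×180 = 8,100.
- SAP: 540 days and 8,100/540 = 15%.
- Reference: 360 days and 8,100/360 = 22.5%.
- Exposure is 50% too high and the average 33% too low.

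**Same start, different stop** (20% on days 1-360, 10% on days 1-90)
- Durations: 360 + 90 = 450 days.
- Numerator: 20×360 + 10×90 = 8,100.
- SAP: 450 days and 8,100/450 = 18%.
- Reference: 360 days and 8,100/360 = 22.5%.
- Exposure is 25% too high and the average 20% too low.

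In these last two logs no pair shares both dates, so the combining rule never applies and all four readings give the same wrong result. In both, the reference average is already below 25%; they show the size of the shift, not a change of target status.

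**One shared boundary day** (25% on days 1-180, 30% on days 180-360)
- SAP: 361 days and 27.51%.
- Reference: 360 days and 27.58%. The difference is trivial.

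**Where the log sum is used.** It feeds the summaries in 8.4.1. The exposure-adjusted adverse event rate (5.21) divides by observation time from study day 1. The annualized event and duration rates (5.11, 5.12) divide by days in the data collection period. None of these uses the log sum.

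**The case against.** The strongest reply is that the SAP already handles the case it foresaw. The rule in 5.16 ends by tying the summed percent to a single duration, which most naturally means one merged record. On that reading the 5.16 and 5.17 averages are correct for identical-date entries. This stands. A reader might infer that two 15% entries over the same days must be reported as 15% instead of 30%, so that an on-target subject appears below target. The documents do not support that as a certain result: it needs durations to be left unmerged in the denominator, which the wording permits but does not require.

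The reply also notes that no overlap is shown to occur. The field is a daily total, which a new regimen would normally replace, and SAP 7.1 sends questionable data for query. This is fair as to frequency. It does not supply a rule for overlaps that remain after query, and the identical-date rule shows that multiple entries were expected.

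Finally, the consequences are bounded. SAP 8.4.1 also derives the percent of calories from the 3-day diet diary and plots prescribed percent over time for each subject, so the log average is not the only evidence on the target. Exposure longer than a subject's time on study would also be noticeable. Both points stand.

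**Conclusion.** The point holds in a limited form and is of low severity. As written, 5.15 counts concurrent days more than once. For partly overlapping entries, exposure is overstated and average dose or percent understated under every reading tested: 540 days and 15% against 360 days and 22.5% in the first assumed log. For identical-date entries, the averages are right on the natural reading and the denominator wording is merely unclear; exposure is right only if 5.15 takes the merged records. Logs without overlap are unaffected.

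The sizes rest on assumed logs and on overlapping entries being true concurrent prescriptions. The documents do not give the share of subjects affected, so the effect on the study summaries cannot be estimated. A reader might also infer that the primary endpoint or the safety rates are distorted. They are not, because sections 5.11, 5.12 and 5.21 use calendar time.

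**What to change.** State one day-based rule and apply it to all three sections:

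- **5.15:** exposure is the number of distinct calendar days covered by at least one log entry, up to the end date that the section already sets.
- **5.16 and 5.17:** the percent or dose on a day is the sum over entries active that day; the average is the mean over distinct covered days.

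Overlapping entries should first be queried under SAP 7.1, because summing is right only if the prescriptions really ran together. An entry left open by mistake needs correcting, not adding.

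The rule leaves non-overlapping logs unchanged and gives the evident intent of the SAP for identical-date entries. It costs a few lines of SAP text and a small programming change, with no new data collection.

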5.17 Overall Average Prescribed UX007 Dose

For each subject, an overall average prescribed UX007 daily dose in mL will be derived using the UX007 treatment log according to the following rules:

- Daily dose will be the field “Total Daily Prescribed Dose” in that entry of the UX007 treatment regimen log for the duration between the start and stop dates when the one log entry has no duplicates with same start and stop date.
- For multiple log entries with same start date and same stop date, the daily dose is the sum of the field “Total Daily Prescribed Dose” of those log entries for that duration.
- Duration is defined as stop date – start date + 1 for each entry in the UX007 treatment log. If a treatment log has a stop date after the specified clinical cutoff date, the duration will be calculated as clinical cutoff date – start date + 1 for each entry in the UX007 treatment log.

Overall average prescribed daily UX007 dose = Sum of (the daily dose * duration) / Sum of duration in the UX007 treatment regimen log

5.18 Overall UX007 dosing completion percentage

For each patient, an overall UX007 dosing completion percentage will be derived using the dosing compliance diary.

- Percent of prescribed UX007 taken will be as entered in that entry of the dosing compliance diary for the duration between the start and stop dates when a single log entry has no duplicates with same start and stop date.
- Duration is defined as stop date – start date + 1 for each entry in the dosing compliance diary. If a dosing compliance diary has a stop date after the specified clinical cutoff date, the duration will be calculated as clinical cutoff date – start date + 1.

Overall UX007 dosing completion percentage = Sum of (percent of prescribed UX007 taken * duration) / Sum of duration of each dosing compliance diary.

5.19 SF-12 PCS and MCS

The SF-12 Health Survey version 2 is assessed for adults 18 years of age and older. Eight domain scores (Physical Functioning, Role Limitations due to Physical Health, Bodily Pain, General Health Perceptions, Vitality, Social Functioning, Role Limitations due to Emotions Problems, and Mental Health) are calculated from raw scores. Additionally two summary component scores are calculated from domain scores (Physical Component Summary Scale [PCS] and the Mental Component Summary Scale [MCS]).

Raw scores range from 0 to 100 with higher scores indicating better health. Domain scores are calculated from raw scores such that domain scores have a mean of 50 and SD of 10. The PCS and MCS summary component scores also have mean of 10 and SD of 10 to allow comparisons with domain scores.

Scoring the SF-12 version 2 is accomplished using T-score Based scoring software from QualityMetric Inc. (Lincoln, RI). T-score Based scoring is standardized across the SF family of adult tools using the means and standard deviations from the 2009 U.S. general population. The T-score Based scores in the U.S. general population have a mean of 50 and a standard deviation of 10. The Medical Outcomes Study (MOS) tools utilize 2009 t-scores.

The main advantage of T-score Based scoring of the adult SF tools is easier interpretation. By using the T-score Based scoring method, your data are scored in relation to U.S. general population t-scores. Therefore, all scores obtained that are below 50 can be interpreted as below the U.S. general population t-score and scores above 50 can be interpreted as above the U.S. general population t-score. Because the standard deviation for each scale is 10, it is easier to see exactly how far above or below the mean a score is in standard deviation units (10 points = 1 standard deviation unit).

5.20 SF-10 PCS and MCS

The SF-10 Health Survey is assessed for children 5 to 17 years of age. Two summary measures (the Physical Summary Score and the Psychosocial Summary Score) are calculated from raw scores to have a mean of 50 and SD of 10.

The T-score based scoring (described in Section 5.19) is also used to score the SF-10 Health Survey for Children summary scales. The scale scores have been centered so that a score of 50 corresponds to the average score in a comprehensive 2006 sample (a combination of general population and supplemental disability and chronic condition samples). Although scale scores are standardized to a mean of 50 and a standard deviation of 10 in the combined U.S. general population and clinical samples, age-specific t-scoreative data should always be used for comparison purposes when results for individual children are being considered or when aggregate data are limited to a specific age range for which t-scoreative data are available.

5.21 Exposure-adjusted Adverse Event Incidence Rate

The exposure-adjusted adverse event incidence rate is defined as the total number of occurrences of an AE summed across all subjects in the group divided by the total observation time for AEs for subjects in that group. The observation time for each subject is the duration from study day 1 (i.e., first dose of UX007) till the end of study period 1 or the date of clinical cutoff, whichever occurs earlier. The total observation time for AEs is the sum of observation times for all subjects in that group.

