7.6.5 Safety Analyses

For the safety analysis, the incidence and frequency of treatment-emergent AEs and SAEs will be evaluated. All AEs will be coded using the Medical Dictionary for Regulatory Activities (MedDRA). The incidence and frequency of AEs will be summarized by System Organ Class (SOC), Preferred Term (PT), relationship to study drug, and severity. A by-subject listing will be provided for those subjects who experience a SAE, including death, or experience an AE associated with early withdrawal from the study or study drug treatment.

Clinical laboratory data will be summarized by the type of laboratory test. The frequency and percentage of subjects who experience abnormal clinical laboratory results (i.e., outside of reference ranges) and/or clinically significant abnormalities will be presented for each clinical laboratory measurement.

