4.4 Safety Endpoints

Safety events will be collected as adverse events (AE) or serious adverse events (SAE).

Primary safety endpoints are incidence and severity of treatment emergent AEs

The other safety endpoints in this study are:

- Vital signs
- Incidence of laboratory abnormalities
- Concomitant medications

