8.7.1 Adverse Events

Adverse events will be coded by system organ class and preferred term using the Medical Dictionary for Regulatory Activities (MedDRA version 23.1). The severity of an AE will be based on Common Terminology Criteria for Adverse Events (CTCAE), Version 5.0. If an AE cannot be graded based on CTCAE, the investigator will assign a severity based on 1 = mild, 2 = moderate, 3 = severe, 4 = life threatening, and 5 = Death.

An AE (classified by preferred term) will be considered a treatment emergent adverse event (TEAE) if it occurred on or after the first dose of UX007 and was not present prior to the first dose or worsening in severity or frequency of a preexisting condition. AEs that started in UX007-CL201 and continued into UX007-CL202 will not be considered UX007-CL202 TEAE since the start date is prior to UX007-CL202 first dose.

The following subject incidence of AEs will be summarized:

- Summary of TEAEs
- TEAEs by SOC and PT (preferred term)
- Related TEAEs by SOC and PT
- Serious TEAEs by SOC and PT
- Serious Related TEAEs by SOC and PT
- Grade 3 or 4 TEAEs by SOC and PT
- Deaths by SOC and PT
- TEAEs leading to discontinuation of study treatment by SOC and PT
- TEAEs by PT
- TEAEs leading to dose reduction by SOC and PT
- TEAEs leading to treatment interruption by SOC and PT
- TEAEs by PT
- TEAEs in the GI SOC
- Related TEAEs in the GI SOC
- GI ADRs
- GI ADRs leading to treatment discontinuation

Hepatobiliary TEAEs (see Appendix 11.4) For those AEs that occurred more than once during the study, the maximum severity or highest grade causality will be used to summarize the subject incidence. Exposure-adjusted adverse event incidence rates will also be presented at the preferred term level.

The number and percent of subjects experiencing one or more TEAE by SOC and PT in order of descending frequency may be summarized by age, gender and subtype of FAOD

history depending on the sample size. The planned age categories are ‘0-1 year’, ‘>1-6 years’, ‘>6-18 years’ and ‘>18 years’ and some may be combined if their number of subjects is small.

In the overall summary of adverse events table, there will be separate summaries for Grade 3 and Grade 4 TEAEs.

Detailed subject listings for all AEs, serious TEAEs, AEs leading to the discontinuation of study, AEs leading to the discontinuation of treatment, and death TEAEs leading to dose reduction, and TEAEs leading to treatment interruption will also be generated.

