8.7.1.1 Gastrointestinal Adverse Drug Reactions

Summaries of gastrointestinal adverse drug reactions (GI ADRs) will be prepared to within each cohort. GI ADRs include the following PTs: Diarrhea, Abdominal pain, Abdominal pain upper, Gastrointestinal pain, Abdominal discomfort, Abdominal distension, Vomiting, and Nausea.

Summaries to characterize the severity and outcome of GI ADRs will include the following:

- 1) incidence of subjects with at least one GI ADR,
- 2) incidence of GI ADRs leading to treatment discontinuation,
- 3) a frequency distribution of the number of GI ADRs per subject,
- 4) descriptive statistics (n, mean, standard deviation, standard error, median and first and 3rd quartiles) for the number of GI ADRs per subject,
- 5) the frequency GI ADRs by severity and seriousness grade
- 6) a frequency distribution of the outcome of the GI ADRs that were
 - a) Recovered/Resolved
 - b) Resolving/Recovering
 - c) Recovered/Resolved with Sequelae
 - d) Death
 - e) Not Resolved

Characterization of the time course of GI ADRs will be provided for:

- 1) Time to first GI ADR with
- 2) Frequency of GI ADRs by time categories
- 3) Number of Subjects with GI ADR by time categories
- 4) descriptive statistics by time categories for any GI ADR

The frequency distributions will the following categories: <= 8 Weeks, > 8 Weeks to <= 24 Weeks, > 24 Weeks to <= 48 Weeks, > 48 Weeks to <= 78 Weeks, > 78 Weeks to <= 102 Weeks, > 102 Weeks to <= 126 Weeks, > 126 Weeks to <= 150 Weeks, > 150 Weeks to <= 198 Weeks, > 198 Weeks to <= 222 Weeks, etc.

The duration of a treatment-emergent GI ADR that was resolved is defined as AE end date minus AE start date plus 1 day. The duration of a treatment-emergent GI ADR for GI events

that are ongoing is defined as data cutoff date minus AE start date plus 1 day. The duration of treatment-emergent GI ADRs will be categorized as follows: 1 Day, 2 to <= 3 Days, 4 to <= 7 Days, 8 to <= 14 Days, 15 to <= 28 Days, and > 28 Days. Descriptive statistics will be also be provided.

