Kaplan-Meier curves will be provided by cohort for time to first treatment-emergent GI ADR which is defined as AE start date minus the first UX007 dose date in UX007-CL202 plus 1 day. For the Kaplan-Meier curves, subjects will be censored at the end of study date or the data cutoff date, whichever is earlier. Time to first GI ADR in a subject is determined by the first GI ADR with non-missing start date of the subject. For the Rollover cohort, only UX007-CL202 data will be used and time plotted will be in weeks since the start of UX007-CL202.

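### The SAP's exposure-adjusted AE incidence rate is an all-occurrence event rate; outside GI adverse drug reactions, TEAE incidence is given only as crude percentages despite unequal follow-up

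*SAP*

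**What the plan says.** SAP 4.4 sets the endpoint: "Primary safety endpoints are incidence and severity of treatment emergent AEs". Protocol 7.6.5 asks for two things: "The incidence and frequency of AEs will be summarized by System Organ Class (SOC), Preferred Term (PT), relationship to study drug, and severity".

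SAP 8.7.1 tabulates subject incidence of TEAEs, overall and by system organ class and preferred term. Each subject counts once: for repeated AEs "the maximum severity or highest grade causality will be used to summarize the subject incidence". It then adds: "Exposure-adjusted adverse event incidence rates will also be presented at the preferred term level".

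SAP 5.21 defines that added measure. It "is defined as the total number of occurrences of an AE summed across all subjects in the group divided by the total observation time". Each subject's observation time "is the duration from study day 1 (i.e., first dose of UX007) till the end of study period 1", or until the clinical cutoff if that is earlier.

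For GI adverse drug reactions (eight preferred terms), SAP 8.7.1.1 goes further: "Kaplan-Meier curves will be provided by cohort for time to first treatment-emergent GI ADR", with censoring at end of study or data cutoff, and "a frequency distribution of the number of GI ADRs per subject".

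Participation lasts up to 84 months (SAP 3.3). SAP 8.5 has analyses presented by cohort unless otherwise specified.

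**The concern.** Within one set of AE outputs, incidence carries two meanings. In the 8.7.1 tables it is one count per subject. In 5.21 it is every occurrence over all observation time. SAP 5.11 calls the same kind of construction, events over time, an annualized event rate when it is applied to major clinical events.

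This has two consequences:

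- A preferred term driven by one subject with many recurrences can show a high incidence rate although few subjects were affected.
- Outside GI adverse drug reactions, the incidence component of the primary safety endpoint has no estimate that takes account of how long each subject was observed. Crude percentages rise with follow-up even when risk is constant, so cohorts with different follow-up can look different for that reason alone.

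**Working it through.** The documents give no AE rate or precision figure for this endpoint, so there is no stated number to reproduce. The check compares definitions and then uses assumed inputs.

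**Definitions**

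- SAP 5.21 rate = all occurrences / total observation time.
- First-event rate = subjects with at least one event / sum of time to first event, or to end of observation if none.
- Crude incidence = subjects with at least one event / N.

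The 5.21 numerator has no first-event restriction and its denominator is not stopped at onset. It is therefore not a first-event rate.

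**Effect of one recurrent subject**

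Assumptions: one non-GI preferred term; N = 150 (Protocol 7.6.6); 4 years of follow-up each; nine subjects with one event and one subject with m events; first events at mid follow-up on average.

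- Total observation time: 150 × 4 = 600 subject-years.
- Time to first event or censoring: 140 × 4 + 10 × 2 = 580 subject-years.
- First-event rate: 10/580 = 1.72 per 100 subject-years for every m.
- Crude incidence: 10/150 = 6.7% for every m.

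| m | SAP 5.21 rate per 100 subject-years | Share of events from one subject |
|---|---|---|
| 1 | 10/600 = 1.67 | 1/10 = 10% |
| 10 | 19/600 = 3.17 | 10/19 = 53% |
| 30 | 39/600 = 6.50 | 30/39 = 77% |
| 60 | 69/600 = 11.50 | 60/69 = 87% |

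For m = 30, removing that subject leaves 9/(149 × 4) = 1.51 per 100 subject-years. With the SAP's N of about 100 (SAP 3.6), the same case gives 39/400 = 9.75, against a first-event rate of 10/(90 × 4 + 10 × 2) = 10/380 = 2.63.

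**Effect of follow-up on crude incidence**

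With a constant first-event hazard h (assumed), crude incidence after T years is 1 − exp(−hT).

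| h per year | 0.5 y | 1.5 y | 3 y | 7 y |
|---|---|---|---|---|
| 0.05 | 2.5% | 7.2% | 13.9% | 29.5% |
| 0.2 | 9.5% | 25.9% | 45.1% | 75.3% |
| 0.5 | 22.1% | 52.8% | 77.7% | 97.0% |

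The documents state only the maximum follow-up of 84 months; the shorter durations are assumed. Follow-up will differ, because a subject's participation can end at 7 years, at commercial availability or at early termination (Protocol 7.1 and 7.3.3), and a clinical cutoff date can truncate it (SAP 5.10.1).

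**The case against.** The case for leaving the plan alone has substance, and several stronger readings fail.

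- **The rate is legitimate.** Protocol 7.6.5 asks for frequency as well as incidence, and an all-occurrence rate supplies frequency. SAP 5.21 states its numerator and denominator plainly. This stands: the measure should be kept, and its name is what needs correcting.
- **A reader might infer that no follow-up-adjusted incidence is planned at all.** SAP 8.7.1.1 contradicts this for GI adverse drug reactions. Diarrhea, for example, is within that group, whose first-event curves and per-subject counts cover most of the problem, though they pool eight preferred terms.
- **A reader might infer that a dominant subject would go unnoticed.** The 5.21 rate sits beside subject incidence by preferred term, and all AEs are listed by subject. Dominance is a risk of misreading, not a certainty.
- **A reader might infer that the denominator is wrong because it can include time after the last dose.** AEs are collected for 30 days after the last dose (Protocol 7.5.5.7), so including that time matches the numerator. Observation time is a sound denominator for an event rate.
- **A reader might infer that a planned cohort comparison is invalid.** SAP 5.6 defines the cohorts for presentation, SAP 8.1 calls the analyses mostly descriptive, and no between-cohort safety test is planned.
- **The constant-hazard illustration will not suit every term.** Protocol 5.3 says that the most frequent treatment-related GI events occurred mostly during up-titration. For events concentrated early, crude incidence would not climb with follow-up as in the table. This stands and limits the illustration.

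**Conclusion.** The point holds as a mislabelled measure and a gap that is cheap to close. SAP 5.21 defines an event rate under an incidence name. Outside GI adverse drug reactions, TEAE incidence has only crude percentages.

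Under the stated assumptions, recurrences in one subject move the 5.21 rate from 1.67 to 11.50 per 100 subject-years (11.50/1.67 = 6.9-fold), while the first-event rate stays at 1.72 and crude incidence at 6.7%. At an assumed hazard of 0.2 per year, crude incidence runs from 9.5% at half a year to 75.3% at 7 years with no change in risk. Event counts, hazards and follow-up distributions are all assumed, so these figures show direction and possible size only.

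The documents do not say that 5.21 is the estimator of the primary safety endpoint or that it is meant to correct the crude percentages. They therefore do not support the reading that the primary safety analysis is invalid.

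**What to change.** 1. In SAP 5.21, rename the measure an exposure-adjusted event rate, state that the denominator is observation time, and keep it for the protocol's frequency aim.
2. In SAP 8.7.1, add a follow-up-adjusted incidence estimate by cohort, for any TEAE and by preferred term. It can be a first-event rate: subjects with at least one such TEAE divided by the summed time from study day 1 to first onset, or to end of observation if none, per 100 subject-years with a 95% CI. Cumulative incidence would also serve, and is the better choice where events cluster early.

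The cost is SAP wording and one extra table column. AE onset dates and observation times are already collected. A first-event rate assumes a roughly constant hazard, which a footnote should state.

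The footnote should also say that CL201 rollover subjects and many in the Other cohort are already exposed at CL202 study day 1, and that AEs continuing from CL201 are not counted as CL202 TEAEs (SAP 8.7.1). A first event therefore means something different in each cohort. The added estimate adjusts for length of follow-up and does not make the cohorts fully comparable.
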